8.5. Recording AEs and SAEs

Severity of AEs will be assessed according to "Division of AIDS table for grading the severity of adult and pediatric adverse events", version 2.0 of November 2014.

Subjects will be asked to report all AEs as part of the procedures performed at each study visit. The site personnel will document all AEs in the subject's medical record. All AEs subsequently must be recorded in the appropriate eCRF sections.

The following points must be recorded for each event:

- A description of the event in medical terms, not as reported by the subject;
- Date of onset (start date);
- Date of resolution (stop date);
- The time of onset with respect to administering the investigational product;
- The severity of the sign/symptom or clinically significant abnormal laboratory value according to CTC AE Classification;
- The causal relationship between the investigational product and the occurrence of each AE. This will be assessed by each investigator using clinical judgment. Alternative causes, such as natural history of the underlying diseases, concomitant medications, other risk factors and the temporal relationship of the event to the investigational product will have to be considered. The causality of all AEs should be assessed by the investigator with the following question: Is there a reasonable possibility that the AE may have been caused by the investigational product? And answered "NO" (if not related) and "YES" (if related);
- Action taken regarding the investigational product:
 - No action;
 - Temporary discontinuation;
 - Permanent discontinuation;
- Subject's outcome:
 - Recovered without sequelae / resolved without sequelae;
 - Recovered with sequelae / resolved with sequelae;
 - Recovering/Resolving;
 - On-going;
 - Fatal (for SAEs only).

If in any one subject, the same AE occurs on several occasions, the AE in question must be documented and assessed anew each time.

8.6. Reporting of SAEs to ABIVAX or its designee

Throughout the study, the reporting of SAEs to the Sponsor or its designee will be done through the SAE forms in the eCRF. In case the electronic SAE reporting system does not work, or after freezing of the subject's eCRF, paper SAE report forms should be used which will be faxed to ABIVAX or its designee.

It is the investigator's responsibility to ensure that the SAE report is submitted to ABIVAX or its designee, within **24 hours after knowledge of the event(s)**. The SAE forms or paper report forms should be completed as thoroughly as possible, with all the available details of the event and signed by the investigator or designee. An assessment of causality should always be provided at the time of the initial report. If the investigator or designee does not have all information regarding the SAE, he/she should not wait to receive additional information before completing the form and notifying ABIVAX or its designee.

Additional or follow-up information relating to the initial SAE report, will be requested, if necessary. Again, this information is to be completed and submitted through the SAE forms within 24 hours of receipt of the information. If the paper SAE report form was used due to technical constraints (see above), the SAE forms in the eCRF should be updated once the system is functional again (and not later than 24 hrs. afterwards), prior to using it to report any additional information. Furthermore, when additional information is received on an SAE after freezing of the subject's eCRF, new or updated information is to be recorded on a paper SAE report form with all the changes signed and dated by the investigator.

In the rare occasion when the electronic system for reporting SAEs does not work and in the absence of facsimile equipment, the investigator should notify ABIVAX or its designee by telephone within the given timeframe, and send a copy of the SAE report form by mail or email.

8.7. Reporting of SAEs to Regulatory Authorities

ABIVAX has a legal responsibility to notify, as appropriate, both the local regulatory authorities and other regulatory agencies about the safety of the investigational product. It is therefore important that the investigator notifies promptly ABIVAX or designee of any SAEs, in order for legal obligations and ethical responsibilities towards other subjects to be met.

In addition, the investigator or designee, will comply with the local regulatory requirements (when applicable) in reporting of SAEs to the ethics committee and, if required, to the relevant government authority.

Safety reports on adverse events that are serious AND unexpected AND associated with the investigational product are prepared according to ABIVAX's policy and applicable regulations and are forwarded to the investigators. These reports are filed with the investigator brochure or other appropriate study documentation. It is the Sponsor or its designee and/or investigator's responsibility to notify the IRB or IEC of these reports, if applicable according to local requirements.

9. DATA ANALYSIS AND STATISTICAL CONSIDERATIONS

A summary of the principal features of the statistical analysis of the data will be described here, in the statistical section of the protocol. A more technical and detailed elaboration of the principal features stated in the protocol will be given in the first version of the statistical analysis plan (SAP).

Any amendments to the SAP will be clearly documented and signed prior to the final database lock including justifications and details of their potential impact on the interpretation of the study results.

9.1. Statistical and Analytical Plans

An interim analysis is planned once the first cohort has completed their last protocol specified visit.

9.1.1. Protocol deviations

Protocol deviations will be reviewed and classed as major or minor during the blind-review meeting. Major protocol deviations are defined as deviations liable to bias the evaluation of the main efficacy endpoint. The following deviations will be considered as major (non-exhaustive list):

- Noncompliance with the inclusion or exclusion criteria;
- Noncompliance with the study treatment;
- Intake of prohibited medication;
- Noncompliance with timewindow.

9.1.2. Definition of study analysis sets

The following datasets will be defined and used for the analyses:

- The **Safety dataset (SAF population)** is defined as those subjects included in the study, who have received at least one dose of the study treatment.
- The **Full Analysis dataset (FAS population)** is defined as those subjects included in the study, who have received at least one dose of the study treatment, and who have at least baseline data.
- The **Per Protocol dataset (PP population)** is defined as those subjects of the FAS population without any major protocol deviation.

9.1.3. Subjects/Subjects disposition

The number and the percentages of subjects enrolled and included in each of the populations will be tabulated. The reason for subject exclusions from each of the populations will also be listed. In addition, the number of discontinued subjects with their reason for discontinuation will be tabulated.

9.1.4. Demographic and other baseline characteristics

Demographics and other baseline characteristics will be summarized by treatment arm. This analysis will be conducted on the FAS population.

9.1.5. Treatment compliance

Treatment compliance/adherence will be summarized by treatment arm. This analysis will be conducted on the FAS population.

9.1.6. Interim analysis

An interim analysis will be produced when the first 12 HIV-positive subjects (Cohort 1) reach day 56 of follow-up. The interim analysis will include the following data: (a) Safety and clinical parameters; (b) HIV-1 RNA, CD4+ and CD8+ counts; (c) Hematology and biochemistry parameters; (d) Pharmacokinetic parameters in plasma, PBMCs and rectal tissue, and (e) Total HIV-1 DNA reservoir in PBMC and rectal tissue.

In addition, regarding the cohort 3, the screening and the D28 viral DNA results should be analyzed immediately once the 12 HIV-positive subjects reach the day 28 time point.

9.2. Efficacy Analysis

All efficacy analysis will be conducted on both FAS population and PP population except if otherwise specified. Descriptive statistics will be presented by treatment arm and include:

- Quantitative variables: mean, standard deviation, minimum and maximum, 95% confidence intervals, median and quartiles will be presented when considered relevant. Number of filled and missing values will also be presented.
- Qualitative variables: count, percentage for each modality and 95% confidence intervals when relevant. Number of missing values will also be presented.

9.2.1. Pharmacokinetics

Individual plasma, PBMC, and tissue concentrations of ABX464 and ABX464-N-glucuronide, will be presented by treatment and time points. Descriptive statistics for the concentrations will be presented as number of available data (N), mean, standard deviation (SD) and will be calculated if at least 2/3 of the values per time-point are above LOQ (i.e. N ≥ 10 if 15 subjects are available for a given group). For descriptive statistics calculations, BLQ concentrations below the limit of quantification will be set to zero (0) if they are reported before the first quantifiable sample or considered as missing data if they are reported after the first quantifiable data.

Then, the following PK parameters will be derived for ABX464 and ABX464-N-glucuronide for each Subjects:

C_{max} , t_{max} : the maximum plasma concentration (C_{max}) and the time taken to reach C_{max} (t_{max}) will be obtained directly from the concentration-time data.

$AUC_{0-\tau}$: the area under the concentration-time curve from time zero to the time of dosing interval τ (24 h post-dose for ABX464 and ABX464-N-glucuronide). If no concentration can be measured at this time point, $AUC_{0-\text{last}}$ (from time zero to the last quantifiable concentration) will be calculated. Both parameters will be presented independently. For both parameters, a linear trapezoidal method will be used.

Individual derived PK parameters will be presented by treatment and day of PK assessment when appropriate. Descriptive statistics of the PK parameters will be presented as N, mean, SD, coefficient of variation (CV %), median, minimum (Min), maximum (Max) values, and geometric mean (GM).

In the tables of individual PK parameters, all the deviations from planned analysis will be mentioned by flagging the abnormal results.

Possible exclusion of flagged PK parameters could be performed if, in the judgment of the pharmacokineticist, they are deemed not to be "pharmacokinetically relevant". Exclusion of PK parameters will be discussed in the PK results section. If data are excluded from the PK dataset, all subsequent statistical analyses will be performed twice, once using the complete available PK dataset and once using the final PK dataset as defined by the pharmacokineticist. Study conclusion will be based on the final dataset as defined by the pharmacokineticist.

For each compound, plasma concentration vs. time curves will be presented on a log-linear scale:

- Mean plots showing the data of both treatments (administration alone and co-administration with ABX464);
- By subject plots with the treatments on separate plots (spaghetti plots).

Formal PK Statistics

Evaluation of drug-drug interaction

The relative bioavailability (F_{rel}) after multiple dose administration with either co-administration of ABX464 will be evaluated on PK parameters determined on Day 28.

The comparison will be performed on C_{max} and $AUC_{0-\tau}$ using a 1-way ANOVA model with treatment as main effect on logarithmically transformed data. For each parameter, a point estimate for the ratio of geometric means (ARTs with 150 mg doses of ABX464) will be obtained by calculating the difference of least square means on the logarithmic scale and subsequent back transformation with the exponential function. Likewise, 90% confidence interval for the ratios will be obtained by back transforming the 90% confidence intervals of least square mean differences on log-transformed PK parameters.

Moreover, evaluation of steady-state will be made by visual inspection of the pre-dose concentration measurement collected over the study duration.

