3. INVESTIGATIONAL PLAN

3.1. Study design

3.1.1. Design and methodology

The ABX464-005 study is a Phase Ib, sequential cohort open label trial designed to provide additional safety and compartmental PK data on ABX464.

The study will also generate exploratory immunological and virological data that combined with the compartmental PK data will help further characterize the mechanism of action of ABX464.

The study will enroll both HIV-infected (N=24) and HIV-uninfected (N=12) study subjects in three distinct cohorts:

- Cohort 1: 12 HIV-infected subjects treated with ABX464 150 mg o.d. for 28 days
- Cohort 2: 12 HIV-uninfected subjects treated with ABX464 50 mg o.d. for 28 days
- Cohort 3: 12 HIV-infected subjects treated with ABX464 50 mg o.d. for 84 days

HIV-infected subjects will add the investigational product to their current antiretroviral regimen whereas the HIV-uninfected subjects will only receive the investigational product.

Cohort 1 will consist of 12 HIV infected subjects. After full enrollment and an interim analysis (including PK and immunological markers) of Cohort 1, Cohort 2 and 3 will begin enrollment and will consist of both HIV infected (n=12) and HIV uninfected (n=12) subjects.

Subjects who successfully complete a screening visit (Visit 1) will advance to a Baseline visit (Visit 2; Day 1). During this visit all subjects will undergo a physical examination and have blood and rectal tissue samples collected.

The rectal tissue samples will be collected before initiating oral dosing with the investigational product (150 mg or 50 mg of ABX464).

After receiving the first dose of ABX464, additional blood PK samples will be collected at 0h, 0.5h, 1h, 1.5h, 2h, 4h, 6h and 8 hours.

All subjects will receive the investigational product once daily for 28 days (Cohorts 1 &2) and for 84 days (Cohort 3).

At Day 28 for subjects enrolled in cohort 3 and at the end of the treatment period (End of Rx Visit; Day 28 for Cohorts 1&2 and Day 84 for Cohort 3) subjects will undergo a physical examination and have blood and rectal tissue collected. PK blood samples will be collected at 0h, 0.5h, 1h, 1.5h, 2h, 4h, 6h and 8 hours.

HIV infected subjects will continue with their antiretroviral regimen i.e. there will be no antiretroviral treatment interruption in this study.

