5.4.8. Pharmacokinetics

Plasma and tissue ABX464 and its metabolite concentrations will be determined by liquid chromatography tandem mass spectrometry (LC-MS/MS) methods validated for all matrices by ATLANBIO.

ABX464

After single oral administration of 50 to 200 mg ABX464, ABX464 is relatively quickly absorbed and undergoes a very extensive biotransformation into its N-glucuronide metabolite, NGlc.

In most of the subjects, regardless of the dose, ABX464 plasma concentration is generally not measured after 8 to 10 h post-dose. Cmax is generally observed within the first 2 h post-dose and then ABX464 plasma concentrations decreased with a $t_{1/2}$ of about 1 to 2 h.

ABX464-N-glucuronide's plasma concentrations were markedly higher than those of the parent drug with mean Cmax about 200 to 300-fold higher than ABX464 Cmax. Cmax was observed around 4 h post-dose with a very limited variability thereafter ABX464 NGlc was slowly eliminated and had a $t_{1/2}$ of 90 to 110 h.

Relationship between rate and extent of absorption of ABX464 and ABX464 dose is quite erratic with a reduced increase with the dose up to 150 mg and saturation like behavior at 200 mg.

ABX464-N-glucuronide's exposure-dose relationship is somehow comparable to that of ABX464 although increase of C_{max} and AUCs tend to be dose proportional between 50 and 150 mg.

Since ABX464 undergoes a high level of biotransformation, ratios between metabolite and parent drug appear to be unchanged across the studied dose range but inter-individual variability prevented from definite conclusions.

Therefore, ABX464 should rather be considered as a pro-drug with regard to its short $t_{1/2}$. Its metabolite, ABX464-N-glucuronide exhibits markedly higher blood concentrations and has a much longer $t_{1/2}$ which could be of pharmacological interest. Last, dose-exposure relationship appears erratic between 50 and 200 mg but tends to linearity up to 150 mg.

ABX464 was shown to have a very short $t_{1/2}$ (1 to 2 h), so steady-state is virtually reached at the second administration, while ABX464-N-glucuronide has a $t_{1/2}$ of 90 to 110 h, meaning that steady-state is reached after 19 to 22 days of administration. Intense PK blood collection is planned to be done on Day 1 (initiation of ABX464 administration) and Day 28 (final dose of ABX464) to characterize accumulation and decay of ABX464 and its metabolite (ABX464-N-glucuronide) in plasma and PBMC.

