Additional blood PK samples will be collected on Days 35 and 56 to characterize the terminal decay of ABX464. In addition, ABX464 and ABX464-N-glucuronide will be quantified in rectal tissue biopsies collected during Visit 2, 6 and 8.

A total of 18 blood samples per HIV negative subjects and 18 blood samples per HIV positive subjects will be collected for PK assessment. These samples will be processed according to the appendix 3 in order to get Plasma and PBMC samples.

Blood samples for determination of ABX464 and ABX464-N-glucuronide, will be collected from all subjects using direct venipuncture or an indwelling catheter.

Then, the following PK parameters will be derived for ABX464 and ABX464-N-glucuronide

- C_{max}, t_{max}: the maximum plasma concentration (Cmax) and the time taken to reach Cmax (tmax) will be obtained directly from the concentration-time data.
- AUC_{0-τ}: the area under the concentration-time curve from time zero to the time of dosing interval τ (24 h post-dose for ABX464 and ABX464-N-glucuronide). If no concentration can be measured at this time point, AUC_{0-last} (from time zero to the last quantifiable concentration) will be calculated. Both parameters will be presented independently. For both parameters, a linear trapezoidal method will be used.

Moreover, evaluation of steady-state will be made by visual inspection of the pre-dose concentration measurement collected over the study duration.

In addition, five rectal biopsies at each time point will be sent to ALTANBIO for tissue PK determination.

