6.3.2. Guidelines for treatment postponement and dose modifications

No intra-subject dose escalation/dose adjustment are allowed.

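### The formal drug-interaction ratio in Protocol 9.2.1 names no reference group, and no cohort can serve as a valid one for the 150 mg dose

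*Protocol*

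**What the plan says.** Protocol 9.2.1, under Formal PK Statistics, sets out an evaluation of drug-drug interaction on Day 28 Cmax and AUC over the dosing interval. The model is a one-way ANOVA on the log scale with treatment as the only factor. From it "a point estimate for the ratio of geometric means (ARTs with 150 mg doses of ABX464) will be obtained", with a 90% confidence interval. The levels of the treatment factor are not defined. The nearest text to a reference is a plotting instruction just above: "Mean plots showing the data of both treatments (administration alone and co-administration with ABX464".

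Protocol 3.1.1 defines three cohorts of 12:

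| Cohort | HIV status | ABX464 dose | ART |
|---|---|---|---|
| 1 | infected | 150 mg | yes |
| 2 | uninfected | 50 mg | no |
| 3 | infected | 50 mg | yes |

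The row that matters most is "Cohort 2: 12 HIV-uninfected subjects treated with ABX464 50 mg o.d. for 28 days". For the infected cohorts, "there will be no antiretroviral treatment interruption in this study". Protocol 6.3.2 adds: "No intra-subject dose escalation/dose adjustment are allowed".

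SAP 10.1 summarises data by cohort, and SAP 11.3.1 summarises the primary PK endpoint descriptively. The SAP contains no ratio or ANOVA for PK, and does not say that the protocol's analysis was dropped.

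**The concern.** An interaction ratio needs the same drug at the same dose, with and without the other drug. The text gives only one side of it, 150 mg with ART, and no subject receives 150 mg without ART. The one formal PK inference in the protocol therefore cannot be run until someone chooses a comparator, possibly after seeing the data, and no choice open to the 150 mg group isolates an ART effect. If Cohort 2 were chosen, a plain dose difference could be reported as an interaction, and a real reduction in exposure could be reported as an increase.

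**Working it through.** **1. Candidate references, one by one.**

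- *Within subject:* ART is not interrupted and the dose is not changed, so no subject has a 150 mg period without ART.
- *Cohort 1 against Cohort 2:* these differ in dose (150/50 = 3-fold), ART and HIV status.
- *Cohort 1 against Cohort 3:* both are on ART, so this is a dose ratio.
- *Cohort 3 against Cohort 2:* same dose, but ART and HIV status differ together. It is also not the 150 mg ratio in the text.
- *ART exposure with and without ABX464* (a possible reading of the plot wording): Protocol 5.4.8 says "Blood samples for determination of ABX464 and ABX464-N-glucuronide, will be collected from all subjects", and Cmax and AUC are derived only for those two analytes. No ART assay or ART-alone profile is described.

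A cohort-level design matrix with columns for intercept, log dose, ART and HIV status has rank 3 out of 4. ART and HIV status coincide in every cohort, so no model on these data separates them.

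**2. What Cohort 1/Cohort 2 would show with no ART or HIV effect.**

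The plan gives no target ratio, CV or power for this comparison, so there is no stated figure to reproduce. Inputs:

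- n = 12 per cohort (Protocol 3.1.1).
- Dose relation from Protocol 5.4.8. For the N-glucuronide, "increase of C_{max} and AUCs tend to be dose proportional between 50 and 150 mg". For the parent drug, the relation is "quite erratic with a reduced increase with the dose up to 150 mg". That section describes single-dose data, so applying it to Day 28 is an assumption.
- Between-subject CVs of 30, 50 and 100%, and parent-drug dose effects of 2.0, 1.73 and 1.5, are assumed because the documents give none. The value 1.73 is 3^0.5.

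Formulas: SE = sqrt(ln(1+CV²)) × sqrt(2/12), and 90% CI = R × exp(±t × SE), with t(0.95, 22 df) = 1.717. At CV 50%, SE = 0.4724 × 0.4082 = 0.1928 and exp(1.717 × 0.1928) = 1.393. For R = 3.0 the interval is 3.0/1.393 to 3.0 × 1.393 = 2.15 to 4.18.

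| Expected ratio from dose alone | 90% CI, CV 30% | 90% CI, CV 50% | 90% CI, CV 100% | Chance CI excludes 1 (CV 100% to 30%) |
|---|---|---|---|---|
| 3.0 (proportional) | 2.44–3.69 | 2.15–4.18 | 1.67–5.38 | 93% to >99.9% |
| 2.0 | 1.63–2.46 | 1.44–2.79 | 1.12–3.59 | 63% to >99.9% |
| 1.73 | 1.41–2.13 | 1.24–2.41 | 0.97–3.10 | 47% to 99.7% |
| 1.5 | 1.22–1.84 | 1.08–2.09 | 0.84–2.69 | 32% to 95% |

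The last column uses the non-central t distribution with non-centrality ln(R)/SE. Excluding 1 is my yardstick, since the protocol sets no bounds. Fitting all three cohorts (33 df, t = 1.692) changes little: 2.16 to 4.16 instead of 2.15 to 4.18.

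**3. Direction.** If ART plus HIV status truly halved metabolite exposure, Cohort 1/Cohort 2 would be expected at 3.0 × 0.5 = 1.5, with a 90% CI of about 1.08 to 2.09 at CV 50%.

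**4. The dose-matched contrast.** Cohort 3/Cohort 2 at Day 28, with no ART or HIV effect, has expected ratio 1.0 and a 90% CI of about 0.81–1.23, 0.72–1.39 or 0.56–1.79 at CV 30, 50 or 100%.

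**The case against.** The strongest reply is about weight. Interaction is neither an objective nor an endpoint, the SAP is already descriptive, and the paragraph refers to two treatments in a three-cohort study, so it may be poorly adapted text that nobody would act on. That limits the harm. But the protocol labels the analysis formal and specifies its model and interval, so it cannot be treated as a slip of wording.

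A reference can arguably be inferred. The safety objective in Protocol 2.2 speaks of ABX464 given alone to uninfected subjects, which would make Cohort 2 the reference in the plots too. That reading is possible, but it leads directly to the ratio that mixes dose, ART and HIV status.

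The figures are also conditional. They need Cohort 2 as the reference, assumed CVs and single-dose information carried over to Day 28, and the halving is only an illustration. All of this is fair. The structural point in step 1 needs none of those numbers.

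Finally, the SAP contradicts nothing in the paragraph; it is silent. But Protocol 9 says the SAP will elaborate the protocol's main statistical features in more detail, so silence leaves it unclear whether the analysis still exists.

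**Conclusion.** The concern holds and should be fixed. As written, the interaction ratio has no denominator, and no cohort or study period supplies a valid one for 150 mg. This follows from the cohort definitions alone. If Cohort 2 were used, dose alone would give an expected ratio of 3.0 under proportionality, or 1.5 to 2.0 under the smaller dose effects assumed for the parent drug. An interval excluding 1 would be likely in most of the settings examined. The size rests on 12 evaluable subjects per cohort, the assumed CVs and dose effects, and the single-dose relation holding at Day 28. The reach is limited to this paragraph and any interaction statement drawn from it.

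**What to change.** Choose one option and make Protocol 9.2.1 and the SAP agree.

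- **Option A (simplest):** delete the interaction analysis and state in the SAP that it was dropped. This costs wording only and fits the existing descriptive plan.
- **Option B (optional):** replace it with Cohort 3 against Cohort 2 at Day 28 on log Cmax and log AUC over 0–8 h, the window covered by the intensive sampling. Report a geometric mean ratio with 90% CI and no decision rule. Label it as the combined effect of ART and HIV status, across several ART regimens and without randomisation, not as a pure interaction. This costs wording plus one programmed contrast on data already planned. Its limits are complete confounding of ART with HIV status and a wide interval (about 0.72 to 1.39 at CV 50% for a true ratio of 1).

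Under either option, remove the parenthesis about ARTs with 150 mg and the co-administration wording in the plot instruction. Present any Cohort 1 against Cohort 3 comparison only as a dose-proportionality summary. Neither option changes dosing, sampling or enrolment.
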